### 3. **Abstract:**

**Background/Purpose:** Falls are a common and costly complication following stroke. While residual walking and balance deficits contribute substantially to long-term disability, of greater concern for this population is the incidence of falls. Between 40% and 70% of individuals fall within their first year post-stroke. Individuals who fall have increased incidence of serious adverse outcomes, including fractures, depression, and mortality. A primary goal of stroke rehabilitation is to improve mobility in the presence of motor, balance, and visual-spatial deficits. The conundrum all stakeholders must face is that increased mobility may increase risk for falls, whereas limiting walking and general mobility will lead to a multitude of deficits associated with inactivity, including recurrent stroke. Because of these serious consequences, there is an urgent need in the rehabilitation of Veterans with stroke to both identify those who are at fall risk and develop intervention strategies that will reduce fall incidence while increasing mobility. Backward walking has recently emerged as both a potential predictor of fall incidence as well as an intervention modality to prevent future falls. However, it has not yet been assessed under the rigors of a controlled trial. We will conduct a randomized controlled trial with three specific aims to examine 1) the effectiveness of Backward Walking Training (BWTraining) early poststroke in decreasing falls, 2) the timing of BWTraining delivery to increase Backward Walking speed (BWSpeed), and 3) the relationship between BWSpeed and prospective fall incidence.

**Subjects:** One-hundred twenty-eight individuals, 2 months post-stroke, will participate. Additional study criteria include: 1) ambulatory with gait speed < 0.8 m/s; 2) community-dwelling; 3) Berg Balance Scale < 42; 4) absence of other neurological conditions; 5) discharged from physical therapy services; 6) stable cardiac status; 7) absence of lower extremity orthopedic impairments or pain that limits gait ability.

**Methods:** Following baseline assessment, participants will be randomized to BWTraining at 2 months (Immediate group) or 1-year post-stroke (Delayed group). The intervention consists of 18 sessions (3X/week for 6 weeks) of BWTraining: 20–30 minutes of step training using a Body Weight Support and Treadmill system (BWST) followed by 15 minutes of overground gait training delivered by a physical therapist-led team. Participants will walk backward overground with assistance as warranted to transfer stepping skills from the BWST environment to overground. The Immediate group will be followed prospectively for 1-year and compared to the Delayed group to determine the effectiveness of BWTraining in decreasing falls (Specific Aim#1). BWSpeed post-intervention will be compared between groups to assess the timing effect of BWTraining (Specific Aim #2). The Delayed group will be followed prospectively for 1-year prior to BWTraining, to determine if BWSpeed at 2-months is a predictor of fall incidence in the first year post-stroke (Specific Aim #3).

Outcome Measures: Fall incidence 2-months to 1-year post-stroke is our primary outcome measure. Secondary measures include forward and backward walking gait speed, dynamic balance measured by the Functional Gait Assessment, fall self-efficacy measured by the Activities-Balance Confidence Scale and gait kinematics.

Data Analysis Plan: The total number of falls per patient month for the immediate and delayed intervention groups will be calculated, and using a nonparametric ratio estimate, point and interval estimates for the average hazard for each group will be determined. The ratio of the two individual group estimates, 95% confidence limits and P-values will be obtained. Forward stepwise ordinal logistic regression will be used to determine the independent relationship between BWSpeed at 2-months post-stroke and 1-year fall incidence of those in the Delayed intervention group.

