
### **Identification of Fall Risk is Necessary to reduce Future Falls.**

Identification of individuals at risk for falling is an important aspect of post-stroke rehabilitation in order to implement pro-active measures both intrinsically (related to the individual) and extrinsically (associated with their environment). Clinical tests of walking speed and postural balance to predict fall risk after stroke have been reported previously. Gait speed has been reported to predict fall risk both in community-dwelling elderly and in individuals post-stroke. A recent, intriguing finding, worthy of further exploration is that backward, more so than forward walking identified, in a cohort of community-dwelling elderly, those that had fallen in the previous 6 months. Walking backward at a speed less than 0.6 m/s identified 100% of fallers and those who walked backward at a speed less than 0.4 m/s had a 3.2 times greater likelihood of being a faller than those who walked faster. In comparison, forward walking velocity at a cut off of 1.0 m/s only identified 83% of fallers. If BWSpeed is a more reliable predictor of falls than forward walking speed in the post-stroke

population is not known. Given the difficulty post-stroke of combining hip extension with knee flexion, necessary to take a backward step, we hypothesize this BWSpeed-fall incidence relationship exists post-stroke as well. Specific Aim 3 will test the hypothesis that BWSpeed at 2-months post-stroke is a significant predictor of fall incidence over the next year 1 year period.

**Backwards walking challenges postural stability in a controlled and safe environment with a dynamic task similar to the type known to induce falls.**

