## **5. Specific Aims:**

**Aim #1:** Test the hypothesis that 1-year fall incidence is decreased for participants randomized to BWTraining administered at 2-months post-stroke (versus usual care comparison group).

**Hypothesis #1a:** BWTraining at 2-months post-stroke reduces the number of falls over the next year.

**Hypothesis #1b:** BWTraining at 2-months post-stroke increases gait speed, improves balance and increases balance confidence over the next year.

**Aim #2:** Test the hypothesis that BWTraining at 2 months (immediate) vs. 1-year (delayed) post-stroke is more effective at improving BWSpeed.

**Hypothesis #2a:** BWSpeed improvement from 2- to 14-months post-stroke is greater when BWTraining is delivered at 2 months versus 1 year post-stroke.

**Hypothesis #2b:** Improvements in forward gait speed, Functional Gait Assessment and Activities-Balance Confidence Scale from 2- to 14-months post-stroke are greater when BWTraining is delivered at 2 months versus 1 year post-stroke.

**Aim #3:** This exploratory aim will test the hypothesis that BWSpeed at 2-months post-stroke is a significant predictor of fall incidence over the next year 1 year period, after adjusting for other covariates.

**Hypothesis #3:** BWSpeed at 2-months will be a significant predictor of fall incidence during the first year post-stroke, after adjusting for other covariates.

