one of the nation's largest inpatient rehabilitation hospitals and stroke is their largest diagnostic category, with approximately 600 stroke admissions per year. Research studies within this entity are conducted under the auspices of their Clinical Research Center. Brooks Rehabilitation Clinical Research Center maintains an IRB-approved registry of individuals who have experienced a neurological injury, approximately 640 individuals with a stroke diagnosis who have signed HIPAA Authorization and can be contacted regarding research trial participation. Potential participants will be contacted via phone and a phone screen will be conducted. The phone screen script is provided in a separate document. If individuals pass the phone screen, they will be invited and scheduled for an in-person screen. Information obtained from the phone screen will only be shared with study personnel and will be stored in a locked cabinet in a locked room. b. Individuals who respond to an IRB-approved advertisement. They will undergo phone screen as above. c. Individuals who signed a Brooks Notice of Privacy Practices upon Brooks admission (which indicates their information may be used for research) will have their medical records reviewed by study personnel and if appropriate will be provided an IRB-approved study flier. If interested, they will have the opportunity to sign the Screening Informed Consent and complete the Screening Assessment while they are an inpatient. If they prefer to wait until they are discharged from inpatient rehabilitation, they will be contacted at six-weeks post-stroke to determine their continued interest and confirm eligibility. Women and members of diverse ethnic and racial groups will be actively recruited.

*Inclusion criteria:* 1) Diagnosis of unilateral stroke, 2)  $\geq 2$  months  $\leq 4$  months post-stroke, 3) Berg Balance Scale  $\leq 42$ , 4) Self-selected 10 meter gait speed  $< 0.8$  m/s, 5) Able to ambulate at least 10 feet with maximum 1 person assist, 6) Medically stable, 7) 18-95 years of age, 8) living in the community, 9) Unilateral lower extremity paresis confirmed by a score of  $< 32$  on the Fugl-Meyer Motor Assessment, 10) Physician approval for patient participation.

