*Training targets*: The overall goal is to enable the participant, by the end of training, to walk independently for a total of 20 minutes in four, 5 minute bouts at 0% BWS with good stepping kinematics. Progression of training will be accomplished by: (1) gradually decreasing BWS from 40% to 0%, (2) initiating treadmill speed just below participant's overground backward walking speed, increasing as able and as tolerated, and (3) providing manual assistance initially when the participant is unable to independently step or control upright posture, and decreasing manual assistance to afford skill and control progression by the participant.

Outcome Measures. Participants' assessments will be stored in a secured study database, password protected, accessible only to study employees. Each participant will be given a study ID with assessments recorded and stored under the study ID. Hard copy folders will be stored in a locked filing cabinet in a locked room with access only available to study personnel.

Participants in both groups will be assessed in parallel throughout the study timeline.

Assessments will be conducted five times according to the study design above:

1. Assessment A (baseline, prior to randomization)
2. Assessment B 6 weeks following randomization
3. Assessment C 6-months post-stroke
4. Assessment D 1-year post-stroke
5. Assessment E 6 weeks following Assessment D.

The assessment battery will be conducted in a 1.5 hour appointment. Assessments are similar to those encountered in physical rehabilitation and should not result in undue fatigue, but participants will be able to rest as needed. All outcome measures will be conducted by licensed physical therapists, blinded to group assignment. The physical therapist will be beside the participant during all physical assessments of gait and balance. All therapists will receive standardized training and will be required to pass a competency exam to ensure standardization of the outcome measure protocol across assessors. Assessments are:

10 Meter Walk Test. Individuals will be given a 3 meter warm-up distance for walking, preceding the 10 meter distance and 3 meters beyond the 10 meters to continue walking. The time that it takes to traverse the 10 meters at the subject's usual pace will be recorded. Participants will walk this distance two times and the speed will be averaged.

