*Power analysis:* The study is powered around Specific Aim 1, comparison of fall incidence at 1-year post-stroke for those in the Immediate versus the Delayed BWTraining groups. Although the analysis is valid for any within patient distribution of the number of falls and time at risk, we must make additional assumptions to calculate power. Dean and colleagues, in a study of post-stroke fall incidence reported an average of 1.5 falls per patient year, and hence we will plan for a 33% reduction from 1.8 falls per year to 1.2 falls per year, with 80% power at  $p=0.05$ . Using a Poisson rate of 1.8 vs. 1.2 falls per year we would require 64 subjects randomized to each group to be followed for one year. Although all data for withdrawals will be used up to the time of withdrawal, we shall recruit an additional 14 subjects (142 total) to assure we observe 128 patient years. We expect the actual distribution of falls to be more compact (less variable) than the Poisson, which allows unlimited falls for a patient. This suggests the real variance within a group will be lower than that suggested in the Poisson, making power a bit higher than stated here. We cannot quantify this, however. Power was derived via large sample approximations, and verified via 10,000 simulations.

All hard copy records will be stored in a locked filing cabinet in a locked office accessible only to study personnel. All electronic data will be stored on a VA secured server. Hard copy data collected at Brooks Clinical Research Center will be transported to the Gainesville VA BRRC via the Principal Investigator in a locked briefcase.

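### Exploratory Aim 3: forward stepwise selection does not guarantee the covariate-adjusted BWSpeed estimate that Hypothesis 3 calls for

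*Combined protocol and SAP*

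**What the plan says.** Section 5 (Specific Aims) labels Aim 3 exploratory: "This exploratory aim will test the hypothesis that BWSpeed at 2-months post-stroke is a significant predictor of fall incidence". Hypothesis 3 then states what is to be tested: "BWSpeed at 2-months will be a significant predictor of fall incidence during the first year post-stroke, after adjusting for other covariates".

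The method appears once, in the Data Analysis Plan paragraph of the Abstract (section 3): "Forward stepwise ordinal logistic regression will be used to determine the independent relationship between BWSpeed at 2-months post-stroke and 1-year fall incidence". That sentence confines the analysis to the Delayed group. The fuller Data Analysis Plan and the power analysis in section 6 deal with Aim 1 only. No section lists the candidate covariates, gives an entry or removal rule, forces BWSpeed into the model, or names a covariate that is always kept.

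The Background subsection on identifying fall risk supplies the obvious comparator. It notes that "Gait speed has been reported to predict fall risk both in community-dwelling elderly" and after stroke, and it treats as an open question the following: "If BWSpeed is a more reliable predictor of falls than forward walking speed in the post-stroke" population.

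**The concern.** Forward selection adds a term only when the data favour it. Two permitted end points therefore fail to answer Hypothesis 3:

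- BWSpeed is not selected, and there is no BWSpeed odds ratio or interval to report.
- BWSpeed is selected and the search stops there, so the reported estimate is unadjusted.

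Forward gait speed, the measure against which the Background sets BWSpeed, need not be in the final model either. A reader of the results could then not tell whether BWSpeed adds anything to a test already in routine use. At stake is whether the Aim 3 result can be interpreted, whichever way it falls.

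**Working it through.** **Sample available.** The documents give no sample size for Aim 3. The Delayed-group size comes from Aim 1: "Using a Poisson rate of 1.8 vs. 1.2 falls per year we would require 64 subjects randomized to each group". That figure reproduces closely. With two-sided alpha 0.05 and 80% power, the difference-of-rates formula gives (1.960 + 0.842)² × (1.8 + 1.2) / 0.6² = 65.4 per group. Power at 64 is Φ(0.6/√(3/64) − 1.96) = Φ(0.81) = 79%. So n = 64 is used below.

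**Can 64 patients carry a small fixed model?** Entry is at 2–4 months and follow-up ends at 1 year post-stroke, so completers contribute about 8–10 months. At 1.8 falls/year the Poisson mean is 1.2 at 8 months and 1.5 at 10 months. Effective ordinal size is n − Σnᵢ³/n².

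| Months | No fall | One | Two or more | Effective size |
|---|---|---|---|---|
| 8 | 19.3 | 23.1 | 21.6 | 56.8 |
| 10 | 14.3 | 21.4 | 28.3 | 55.4 |

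That is about 14 per term with BWSpeed plus three covariates (55.4/4 to 56.8/4), and 18–19 with two.

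**How often does stepwise miss the target?** The following are assumptions, because the documents give none of them: five candidates (BWSpeed, forward speed, Berg, one more mobility measure, age), likelihood-ratio entry at p<0.05, follow-up uniform on 8–10 months, 10% early withdrawal, 5% of falls injurious, and 2,000 datasets per setting. The outcome is the three fall categories in section 6. The forced model contains BWSpeed, forward speed, Berg and age. Setting 1 makes BWSpeed the only true predictor (rate ratio 0.61 per SD). Setting 2 adds an effect of forward speed (log rate −0.3 per SD). Columns are the correlation among mobility measures.

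| | 0.3 | 0.5 | 0.7 |
|---|---|---|---|
| Setting 1: stepwise omits BWSpeed | 7% | 11% | 21% |
| Setting 1: forced BWSpeed non-significant | 9% | 17% | 36% |
| Setting 2: stepwise omits BWSpeed | 10% | 18% | 33% |
| Setting 2: forced BWSpeed non-significant | 12% | 23% | 43% |
| Setting 2: forward speed absent from models containing BWSpeed | 51% | 69% | 86% |

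A repeat run of both settings gave omission in 6–34%. In setting 1, BWSpeed stands alone in 80–84% of the models that contain it; over both settings the range is about half to nearly 90%.

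A second simulation used different assumptions (BWSpeed plus five covariates, correlation 0.3 or 0.6, 300 runs each). With log odds ratios of 0.5 for BWSpeed and for one covariate, BWSpeed was omitted in 48% and 59% of runs, alone in 29% and 32%, and adjusted for anything in only 23% and 9%.

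**Is the coefficient distorted?** The entries are median BWSpeed coefficients divided by the adjusted value, which is the forced model fitted to 200,000–300,000 simulated patients. The last two rows of each block come from a repeat of 500 datasets.

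| | 0.3 | 0.5 | 0.7 |
|---|---|---|---|
| Setting 1: stepwise, when entered | 1.08 | 1.09 | 1.13 |
| Setting 1: forced, all samples | 1.07 | 1.06 | 1.05 |
| Setting 1: stepwise, repeat | 1.09 | 1.09 | 1.13 |
| Setting 1: forced, significant only | 1.12 | 1.17 | 1.35 |
| Setting 2: stepwise, when entered | 1.13 | 1.25 | 1.43 |
| Setting 2: forced, all samples | 1.07 | 1.07 | 1.05 |
| Setting 2: stepwise, repeat | 1.13 | 1.26 | 1.49 |
| Setting 2: forced, significant only | 1.11 | 1.19 | 1.37 |

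Read only when significant, the forced model is inflated more than stepwise in setting 1 and slightly less in setting 2.

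**False positives.** With no independent BWSpeed effect, stepwise enters it in 4–11% of samples, and the forced test rejects in 5–7%.

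**The case against.** The strongest reply is that the plan may intend covariates to be selected around a retained BWSpeed term. The Abstract speaks of an independent relationship, Hypothesis 3 of adjustment, and the outcome section singles out BWSpeed as the variable of interest. That reading is plausible, but it is written nowhere, and it would still let forward speed drop out. If it is the intention, stating it closes half the gap.

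Second, the numerical harm depends on assumed effects. This stands. Forward speed and Berg score are both restricted at entry (for example, "Self-selected 10 meter gait speed" must be below 0.8 m/s), so how well either predicts falls in this sample is unknown. The two defective end points follow from the method itself; only their frequency is assumed.

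Third, a reader might infer more than the documents support:

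- *Lost power.* In both settings the forced model is non-significant more often than stepwise omits BWSpeed.
- *More false positives.* The excess is small at most.
- *A badly biased coefficient.* Setting stepwise results, seen only when BWSpeed enters, against forced results from all samples is not like for like. Most of the gap is selection on significance. Interval coverage computed only on entered models has the same flaw.
- *Far higher omission under overdispersion.* A dispersion of 0.8 raises omission to 36–49%, but the power section expects falls to be less variable than Poisson.
- *Bias from unequal follow-up.* Omitting log exposure moved the forced coefficient only 2–7% towards zero, so no material bias is shown. The outcome categories are evidently the three defined under Fall Incidence. Neither warrants a recommendation.

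**Conclusion.** The point holds as a minor one. The stated procedure does not secure the quantity in Hypothesis 3, because it can give no BWSpeed estimate or an unadjusted one. At n = 64 with Poisson counts and the assumed effects, omission occurs in roughly 6–34% of samples, and a lone BWSpeed term makes up about half to nearly 90% of the models that contain it. These rates rest on assumed effects, correlations, candidate list and entry level, and the second set of assumptions gave higher omission. The gap in the text is certain; its numerical size is illustrative.

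The cost is interpretability: there is no adjusted estimate and interval that is reported regardless of significance. Aim 3 is exploratory, and the Aim 1 comparison is unaffected.

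**What to change.** For the Delayed group, specify one ordinal logistic model that always contains continuous BWSpeed and two or three baseline covariates named in advance from those already collected, for example forward gait speed, Berg score and age. Report the BWSpeed odds ratio and 95% CI whatever its p-value. Any stepwise search becomes supplementary.

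The cost is a change of wording, with no new data. The covariate set should stay small: with six forced terms, the likelihood-ratio test rejected in 8–10% of runs when BWSpeed had no independent effect.

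There are two downsides. Other candidate predictors become descriptive. The adjusted estimate will also be imprecise: the median standard error of the log odds ratio was 0.32–0.43 in setting 2, so the limits lie a factor of exp(1.96 × 0.32) = 1.9 to exp(1.96 × 0.43) = 2.3 either side of the odds ratio.

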#### **4. Background:**

##### **Falls are a Common and Serious Complication after Stroke.**

Stroke is the leading cause of chronic disability world-wide and in the United States more than 795,000 persons experience a new or recurrent stroke each year. Impairments of motor control and the subsequent functional limitations in ambulation ability are the most common manifestations of stroke. Falls among community-dwelling individuals with stroke are widely reported in the literature, with incidence of falls reported to be 40% and 70%. When tracked over a period of four to six months, community-dwelling individuals with stroke were two times more likely to fall than the average elderly population. Individuals post-stroke have a higher fall risk secondary to persisting neurological impairments such as motor, sensory and vision deficits. These deficits can directly affect balance and mobility, thereby increasing fall risk.

The consequences of falls can have a negative physical and psychosocial impact for individuals post-stroke. Physical injuries following a fall for those post-stroke include both fractures and soft tissue injuries with overall injury incidence reported to be 15%-50%. Hip fractures are the most common fractures reported; a 2.1% rate of hip fractures has been reported to occur in individuals with stroke after a fall. There is a two-to four-fold increase in the risk of hip fractures in individuals with stroke than in those without. Negative psychosocial impact of falls on individuals with stroke include fear of falling, reduced mobility, greater disability, depression, increased stress experienced by the caregiver, and social isolation. Fear of falling often leads to activity restriction as reported by Mackintosh et al., who determined that 44% of individuals post-stroke restricted their activities due to fear of falling. Belgen reported that individuals with stroke who fell were 5.6 times more likely to be afraid of falling. This fear of falling leads to reduced falls-related self-efficacy, resulting in a loss of functional independence. Community-dwelling individuals with stroke who have fallen have also been found to be less socially active and more depressed. Depression and reduction in social activity can result in further deconditioning and reduction in physical activity, further increasing the risk of falls in these individuals. Given this devastating cascade of events that can occur following a fall in this population and the enormous health-care dollars associated with a fall and its potential sequelae, there is an urgent need to develop rehabilitation strategies that will decrease fall incidence in individuals post-stroke. Specific Aim 1 will examine the efficacy of BWTraining to decrease fall incidence in the first year post-stroke.

